Application will be made to CMS for reimbursement consideration. Subject's health insurance will be billed for costs that are part of usual medical care. Any co-payment, co-insurance or deductible, will be the responsibility of the subject. There are no extra costs to subjects for participating in this research study. The pre-discharge transthoracic echocardiogram required for the study (treatment arm only) will not be billed to the subject or their insurance.

Consent Process

Once a subject has been identified as meeting criteria for the study, the PI and/or other delegated study personnel will explain the study in detail to the subject. This discussion will take place in privacy at Spectrum Health. Adequate time will be allowed for questions. A copy of the consent will be given to the subject to read and review. After allowing the subject adequate time to review the consent, the research coordinator will answer any additional questions and ensure that the subject realizes participation is voluntary. A signed copy of the informed consent will be given to the subject.

Sharing of Results with Subjects

There are no plans to share research results with subjects.

References

- 3. Atrial Fibrillation After Cardiac Surgery ed. Jonathan Steinburg 2007 Springer Science & Business Media

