- 1. Control arm: Elective open heart surgery without a limited left sided maze procedure.
- 2. Treatment arm: Elective open heart surgery with a limited left-sided maze procedure.

Sample Size Determination

No sample size calculation was performed as this is a feasibility trial and the number is fixed at 60 patients where 30 will be randomly assigned to the control arm and 30 randomly assigned to the treatment arm.

Statistical Methods

Summary statistics will be calculated. Quantitative variables will be expressed as mean ± standard deviation or median [interquartile range]. Qualitative variables will be expressed as frequency (percent). To determine if there is an association in POAF and the two arms of the study, a Chi-Square Test or Fishers Exact test will be used depending on assumptions being met. To look at our secondary outcomes such as hospital length of stay and incidence of postoperative reoperations for bleeding, a two sample t-test or Wilcoxon Rank Sum will be used to determine if there is a difference between the two groups and those that had POAF vs. those that didn't. Significance will be assessed at the 0.10 level. A level of 0.10 will provide more power to the study while only allowing a slight increase in error.

Recruitment methods

All subjects who receive an inpatient or outpatient heart surgery consult and meet the criteria may be approached about study participation. Consults will occur in the Cardiothoracic Surgeon's office of the Meijer Heart Center or Spectrum Health inpatient units. The subject's electronic medical records (EMR), Cerner and Epic, will be reviewed. There are no plans for advertisement or patient payment related to study participation.

It is expected enrollment will take approximately 6 months.

Inclusion and Exclusion criteria

Inclusion Criteria

- 1. Male or female
- 2. Age \geq 70 years
- 3. Elective cardiac surgery: isolated AVR, isolated CABG, or AVR/CABG,

Exclusion Criteria

- 1. A history of AF or atrial flutter
- 2. Less common cardiac operations such as aortic root replacements, aortic dissections, myxoma excisions, or pericardectomies. Beating heart or off-pump procedures, redo open heart procedures.
- 3. Subjects with existing pacemaker and/or AICD
- 4. Vulnerable populations; adults unable to sign consent, prisoners
- 5. Need for emergent or salvage surgery for any reason
- 6. Currently participating in an investigational drug or another device study (excluding registries)

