Postoperative monitoring, diagnostic and lab tests will be done according to Spectrum Health standard of care. Current standard of care for the postoperative cardiac surgery patient at this institution consists of continuous telemetry monitoring, collection of arterial blood gases, complete blood count, basic metabolic panel and blood glucose at regular intervals. An EKG is obtained on arrival to the recovery area and any time a cardiac dysrhythmia is noted.

In addition to standard of care, subjects who were randomized to the treatment arm of the study will have a pre-discharge transthoracic echocardiogram to assess the absence or presence of thrombus in the left atrium. If thrombi are noted, subjects will be anticoagulated per standard of care.

The highest risk of POAF is within the first 48 to 96 hours after surgery. All post-operative patients are on continuous 24 hour telemetry after surgery until hospital discharge. While it depends on the index procedure that was done, the usual length of stay at this institution following elective cardiac surgery is 5 to 7 days.

If subjects develop POAF, paroxysmal or sustained, they will be treated with standard medications and protocols already in place for this complication.

The current protocol to treat POAF first entails escalation of beta blocker therapy if it is tolerated. If further treatment is necessary, patients are loaded with a dose of IV amiodarone and then changed to oral amiodarone for four weeks or longer if appropriate.

Our current standard of care at Spectrum Health for POAF anticoagulation is as follows. For POAF that persists for more than 24 hours or is episodic and occurs more than once, anticoagulation is initiated. Warfarin or one of the new oral anticoagulants such as dabigatran, rivaroxaban or apixiban will be used tailored to the individual patient utilizing their CHA2DS2-VASc score and surgeon preference.

In addition, all patients who receive a mechanical valve or a bio prosthetic mitral valve are started on an anticoagulant on postoperative day 2. The dose is titrated to an INR of 2.5-3.5.

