- Medications, pre- and post-op including name of medication, indication, dose.
- Procedure and date- including number of grafts and type of valve implanted
- CPB time, X-clamp time
- EKG rhythm(s), pre- and post-op (atrial flutter, SVT, VT, etc.)
- Post procedural stroke/TIA
- Post procedural MI
- Post procedural pacemaker implant
- Any bleeding complication
- Any incidents of POAF (date occurred, treatment used,)
- Length of stay

Data will also be collected at 6 weeks, 6 months and 12 months post-procedure. This will include:

- All adverse events
- Any rehospitalizations
- Medications, current and new
- Any episodes of AF or other cardiac arrhythmias
- EKG
- Need for pacemaker

• Echocardiogram: EF, valve gradients, left and right atrial function, pulmonary vein stenosis or presence of suspected thrombus.

In the event that we are unable to find subject information in the EMR at appointed study intervals, we may telephone subjects to inquire how they are and whether or not they have had any adverse events.

Assessments/procedures	Baseline	Hospitalization	Predischarge	Follow up	Follow up	Follow up
	Screening			6 weeks	6 months	12 months
				post	post	post
				procedure	procedure	procedure
				+/-7 days	+/- 7 days	+/- 7 days
Consent	Х					
History/Inclusion and	Х					
Exclusion						
Medication Review	Х	X		X	X	X
Randomization	Х					
AF occurrence and		X		X	X	X
treatment						
Transthoracic echo			X			
			Treatment			
			arm only			
Rehospitalizations				X	X	X
Adverse Events		X		X	X	Х

Adverse events

An adverse event (AE) is any untoward medical occurrence (signs, symptoms, abnormal laboratory findings) in a subject. It does not necessarily have to be caused by the device or procedure to be considered an adverse event.

A serious adverse event is one that led to death, serious deterioration in the health of the subject, resulted in a new hospitalization or prolonging the index hospitalization, a permanent impairment of a body structure or function, or required medical and/or surgical intervention to prevent further lifethreatening illness or injury

A device related adverse event is an event that in the investigators judgement may be related to the investigational device.

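### Length of stay may be tested by t-test or Wilcoxon with no stated rule for choosing, and neither allows for the operation; the cost is precision and an open choice of test, and its size depends on a spread the documents do not give

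*Combined protocol and SAP*

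**What the plan says.** All places are in the combined protocol and SAP.

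- **Statistical Methods, POAF.** The choice of test is tied to a condition: "a Chi-Square Test or Fishers Exact test will be used depending on assumptions being met".
- **Statistical Methods, secondary outcomes.** For LOS, "a two sample t-test or Wilcoxon Rank Sum will be used to determine if there is a difference between the two groups". No condition is attached. "Significance will be assessed at the 0.10 level"; sidedness is not stated.
- **Sample Size Determination.** "No sample size calculation was performed as this is a feasibility trial and the number is fixed at 60 patients", of whom "30 will be randomly assigned to the control arm and 30 randomly assigned to the treatment arm".
- **Study endpoints.** LOS is named as a secondary endpoint.
- **Procedures Involved in the Research.** "While it depends on the index procedure that was done, the usual length of stay at this institution" is given as 5 to 7 days. Randomisation is 1:1 in REDCap before surgery, and no stratification is described.
- **Inclusion and Exclusion criteria.** Three operations are enrolled: isolated AVR, isolated CABG and AVR/CABG.
- **Data management.** The operation is recorded: "Procedure and date- including number of grafts and type of valve implanted".
- **Study Design.** The trial is unblinded.

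No stratified or covariate-adjusted analysis appears anywhere. This point covers only the comparison of LOS between the randomised arms, not the other outcomes or the POAF versus no-POAF comparison in the same sentence.

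**The concern.** Shorter stay is one of the main benefits the Background claims for preventing POAF, which it says lengthens the stay by two to four days on average. LOS is therefore likely to be read closely.

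Two things are left open. First, the t-test and the Wilcoxon test respond differently to a few very long stays, and a plan that permits both without a criterion lets the verdict depend on a decision made after unblinded data are visible. Even with no intent to select, the stated 10% error rate belongs to one fixed test, not to a choice between two. Second, the protocol says LOS varies with the operation, which is planned before randomisation and recorded. Leaving it out keeps avoidable variation in the comparison.

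**Working it through.** **No figure to reproduce.** The plan gives no LOS effect size, spread or power.

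**Inputs from the documents.** 30 per arm; alpha 0.10 (taken as two-sided, since the plan speaks of a difference); usual stay 5 to 7 days; POAF adds 2 to 4 days (3 used); POAF risk 30% (a minimum), 40% and 60% for CABG, AVR and AVR/CABG (Background); target population at 40% or more (Study Design).

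**Assumptions.** Typical stay 5, 6 and 7 days for CABG, AVR and AVR/CABG; operation mix; spread; share of very long stays; size of the POAF reduction.

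**Step 1: how large a saving is plausible.** Mean days saved through POAF = absolute POAF reduction × days per case.
- 40% to 10%: 0.30 × 3 = 0.90 day.
- Risks 30/40/60%, equal mix: average 43.3%. A 75% cut saves 0.433 × 0.75 × 3 = 0.98 day; a 50% cut saves 0.65 day.
- Same risks, mix 60/20/20: average 38%. The savings are 0.86 and 0.57 day.

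Closed-form power is Φ(δ / (σ√(2/30)) − 1.645). For δ = 1.0 and σ = 2 days: Φ(1.936 − 1.645) = 61.5%. For δ = 0.6 and σ = 4: Φ(0.581 − 1.645) = 14.4%. Power for LOS is limited whichever test is used.

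**Step 2: simulation with long stays.** LOS = operation median × lognormal, + 3 days if POAF, + 10 to 25 days in a few patients, rounded to whole days. Mix 60/20/20, POAF 40% vs 10%, 8,000 trials per setting. A t-test and a Wilcoxon test disagree in 2 × (either significant) − (t) − (Wilcoxon) of trials.

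| Long stays, log-SD | t-test | Wilcoxon | van Elteren | Either of t, Wilcoxon | Disagree |
|---|---|---|---|---|---|
| 5%, 0.25 | 23.4% | 42.3% | 44.6% | 45.5% | 25.4% (counted directly) |
| 5%, 0.35 | 21.7% | 34.9% | 36.0% | 38.2% | 2 × 38.2 − 21.7 − 34.9 = 19.8% |
| 3%, 0.25 | 29.3% | 44.4% | 47.3% | 47.7% | 2 × 47.7 − 29.3 − 44.4 = 21.7% |

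Under no effect (first row's setting) the t-test, Wilcoxon and van Elteren tests reject in 10.2%, 9.9% and 9.8% of trials; taking the smaller of the t and Wilcoxon p-values rejects in 14.7%. Over all long-stay settings and repeat runs the ranges are about 21% to 29% (t), 34% to 44% (Wilcoxon), 18% to 25% disagreement and 13% to 15% false positives. Without long stays the same model gives similar power for the two tests, about 8% disagreement and about 11% to 12% false positives.

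**Step 3: a second model.** POAF risk 30/40/60% by operation, equal mix, POAF cut by 75%, 5,000 trials per setting. SD is the base SD in days, before POAF is added.

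| LOS shape | t-test | Wilcoxon | van Elteren | Disagree | Smaller p, no effect |
|---|---|---|---|---|---|
| Normal, SD 2 | 41.8% | 40.6% | 44.0% | 5.5% | 11.6% |
| Lognormal, SD 2 | 43.8% | 43.6% | 46.4% | 8.5% | 11.6% |
| Lognormal, SD 3 | 28.5% | 31.9% | 32.4% | 10.2% | 12.9% |
| Lognormal, SD 2, plus 5% very long stays | 28.3% | 38.3% | 41.3% | 17.0% | 14.1% |

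With a 50% cut the last row becomes 17.5%, 22.9%, 23.9% and 11.6% disagreement.

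**Step 4: what stratifying adds.** In the second model, over both mixes, both POAF cuts and direct shifts of 1 or 2 days, the gain of van Elteren over Wilcoxon runs from 0.4 points (18.7% to 19.1%) to 5.1 points (84.5% to 89.6%). If the operation has no effect on LOS, stratifying costs about 1 to 2 points.

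**Step 5: smaller effects.** In the first model with 5% long stays, POAF 40% vs 19% gives t-test 16% to 17%, Wilcoxon 22% to 26% and disagreement 15% to 17%. POAF 40% vs 32% gives 10% to 11% and 12% to 13%, so neither test detects anything.

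**The case against.** **The choice of test is implied.** The preceding sentence ties the POAF test to its assumptions, and "Quantitative variables will be expressed as mean ± standard deviation or median [interquartile range]" runs parallel to the t-test and Wilcoxon pair. The natural reading is choice by distribution. That is fair, but the text does not say so for LOS, and even on that reading no check or threshold is named. A reader might go further and infer that the team means to pick the favourable test; nothing in the documents supports that.

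**The long tail is not documented.** A reader might take it as given that LOS is strongly skewed here and that the tests will often disagree. The protocol states only the usual stay; it gives no spread, skew or long stays. This objection stands, and the larger figures are conditional on it.

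**The effect is generous.** 40% to 10% is a 75% relative cut. The cited randomised-style comparison of prophylactic pulmonary vein isolation in CABG (Risks/Benefits to Subjects) is reported as a 21% reduction, which could be absolute (40% to 19%) or relative (40% × 0.79 ≈ 32%). Step 5 shows the differences shrink accordingly.

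**Stratification matters little.** This also stands. Gains of 4 to 10 points appear only if AVR/CABG has a 9-day median, outside the protocol's 5 to 7 days. With a 60/20/20 mix AVR/CABG would have about 12 patients, and in about 23% of simulated trials one arm had three or fewer. Omitting the operation does not bias a randomised comparison, so a reader should not infer bias.

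**It is a secondary endpoint of an unpowered feasibility study.** True, and this limits the severity. But the plan itself chose a formal LOS test at 0.10, so the test should be defined.

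**Conclusion.** The point holds as a matter of precision and of an unfixed choice of test. It does not show bias in the arm comparison and does not touch the primary POAF analysis.

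The open choice is the main part. Its size rests on undocumented assumptions about spread, long stays and operation mix. With 3% to 5% very long stays and POAF cut from 40% to 10%, choosing the t-test gives up roughly 13 to 19 points of power against the Wilcoxon in the three settings tabulated in step 2 (for example 34.9 − 21.7 = 13.2 and 42.3 − 23.4 = 18.9), and a free choice raises the false-positive rate from 10% to 13% to 15%. Without long stays the tests have similar power and the inflation is about 1 to 2 points, reaching about 3 in the wider lognormal setting of step 3. Ignoring the operation costs about 0 to 5 points if the operation medians lie within 5 to 7 days. The change is worth making because it is cheap, not because the harm is proven large.

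**What to change.** In Statistical Methods, replace the either/or for the arm comparison of LOS with wording such as: *Length of stay will be compared between the randomised arms by a two-sided Wilcoxon rank-sum test stratified by planned operation (van Elteren; isolated CABG, isolated AVR, AVR/CABG) at the 0.10 level. Median and mean length of stay will be reported by arm, with a 90% confidence interval for the difference in mean days from a bootstrap stratified by operation.*

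The mean difference is the right estimate of days saved, since the stated benefit is average days and cost. An unstratified Hodges-Lehmann shift would not match the stratified test. With whole-day stays it also came out at exactly 0 or 1 in about 77% to 85% of simulated trials, where the true mean saving was 0.9 day.

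Cost: two sentences, no new data and no change to the trial's conduct. The downside is about 1 to 2 points of power if LOS does not vary by operation, and a rank-test p-value that may not agree exactly with the interval for the mean difference. The wording should acknowledge the latter.

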Prophylactic Limited Left Sided Maze Procedure to Prevent Post-Operative Atrial Fibrillation in Adult Cardiac Surgery Patients

(PREVENT AF-Feasibility Study)

Investigator: [name], FACS

CV Cardiothoracic Surgery

Spectrum Health [name]

Version Date: February 17, 2020

Objective

To evaluate the safety and effectiveness of a prophylactic limited left sided maze procedure in subjects undergoing cardiac surgery to decrease the incidence of post-operative atrial fibrillation (POAF).

Background

Atrial fibrillation (AF) is the most common complication following adult open heart surgery and is the leading cause for prolonged hospital stay (1,2). The incidence of this common post-operative complication is 30 to 60% (1,25). POAF places enormous strain on hospital resources and subjects' immediate post-operative wellbeing. More importantly, patients who experience POAF have decreased long-term survival (33,34). Currently there is no effective treatment to prevent POAF (25,26). Although multiple preventative therapies have been trialed the overall incidence remains at around 40% (Society of Thoracic Surgeons Database 2017). New treatment strategies are needed to reduce or eliminate the occurrence of POAF. An effective strategy would lessen the associated morbidities such as hypotension and heart failure, exclude the additional medications especially anticoagulants, and negate the added hospital length of stay (LOS) incurred by this complication.

AF is an abnormal and irregular heart rhythm in which electrical signals are generated chaotically throughout the upper chambers (atria) of the heart. Studies have demonstrated increased risk factors for the development of POAF (11,12,15). The predominant risk factor is age. Age 70 or greater predicts a minimum 30% risk of POAF with isolated coronary artery bypass grafting (CABG) surgery (11,12,15,18). An isolated aortic valve replacement (AVR) in this age group carries a 40% risk while a combined AVR/CABG, MVR (mitral valve replacement)/CABG or AVR/MVR have a 60% risk of POAF (18,25). Although there are other published risk factors which increase the occurrence of POAF such as low ejection fraction, peripheral arterial disease, diabetes, chronic obstructive pulmonary disease, or renal failure; they are not consistent throughout the literature (11,12,15,18).

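### Length of stay is tested, unadjusted, by POAF status as well as by arm; operation type is linked to both, so a difference cannot be attributed to POAF

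*Combined protocol and SAP*

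**What the plan says.** Statistical Methods names the "secondary outcomes such as hospital length of stay and incidence of postoperative reoperations for bleeding" and says that a two-sample t-test or Wilcoxon rank sum test "will be used to determine if there is a difference between the two groups and those that had POAF vs. those that" did not. One sentence thus covers two comparisons: between the randomised arms, and between patients who did and did not develop POAF. The next sentence applies to both: "Significance will be assessed at the 0.10 level". No covariate is named, and nothing marks the second comparison as descriptive or exploratory.

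Other parts of the protocol bear on it:

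- **POAF risk by operation (Background).** For patients aged 70 or over the risk is at least 30% for isolated CABG; "An isolated aortic valve replacement (AVR) in this age group carries a 40% risk"; the combined AVR/CABG operation carries 60%. All three operations are eligible.
- **Stay by operation (Procedures Involved in the Research).** The usual stay is given as 5 to 7 days and is said to vary with the index operation.
- **Monitoring (same section).** "All post-operative patients are on continuous 24 hour telemetry after surgery until hospital discharge". The sentence before it puts the peak of POAF risk at 48 to 96 hours.
- **Size.** Under Sample Size Determination, "the number is fixed at 60 patients where 30 will be randomly assigned to the control arm and 30 randomly assigned to the treatment arm".
- **Allocation.** Randomisation is 1:1 before surgery; no stratification by operation is stated.

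**The concern.** The arm comparison is protected by randomisation. The POAF comparison is not, because its groups are formed by an event after surgery. By the protocol's own figures, the POAF group will hold a larger share of combined operations and a smaller share of isolated CABG than the non-POAF group. If stay also varies with the operation, as the protocol says, the two groups will differ in stay even if POAF adds nothing to it.

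The comparison also pools the arms. The maze is meant to lower POAF, and the risk section lists bleeding and added bypass time among its possible harms. Arm could therefore also be related to both sides of the comparison.

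What is at stake is interpretation. Background states as fact that POAF lengthens stay by two to four days and builds an economic argument on it. A significant result in this trial could be taken as local confirmation, which an unadjusted test cannot give.

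**Working it through.** The plan gives no power, effect size or error rate for this comparison, so there is no figure to reproduce. The check asks how often the planned test would be significant if POAF had no effect on stay.

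**Inputs from the protocol.** 60 patients, 30 per arm; level 0.10; POAF risks of 30%, 40% and 60% for CABG, AVR and combined (the CABG figure is a stated minimum); usual stay 5 to 7 days, varying with the operation.

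**Assumptions.** Two-sided testing; SD of stay 2 days within operation; mean stays of 5/6/7 days (operations spread over the whole stated range) or 6/6.5/7 days (half that spread); operation mix 33/33/33, 50/20/30 or 70/15/15%; the maze leaves POAF risk unchanged or halves it.

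**Spurious gap by hand: equal mix, 5/6/7 days, maze without effect.**

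- Mean stay with POAF = (0.3×5 + 0.4×6 + 0.6×7) / (0.3 + 0.4 + 0.6) = 8.1/1.3 = 6.23 days.
- Mean stay without POAF = (0.7×5 + 0.6×6 + 0.4×7) / (0.7 + 0.6 + 0.4) = 9.9/1.7 = 5.82 days.
- Gap = 0.41 day, produced by operation mix alone. With 6/6.5/7 days it is half that, 0.20 day.

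**Rejection rate by normal approximation, same case.**

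- Expected POAF rate = 1.3/3 = 43.3%, so about 26 patients with POAF and 34 without.
- Variance of stay = 2² + variance of the operation means (2/3) = 4.67; SD = 2.16.
- Standard error = 2.16 × √(1/26 + 1/34) = 2.16 × 0.2605 = 0.563.
- Gap/SE = 0.407/0.563 = 0.72.
- P(significant) = P(Z > 1.645 − 0.72) + P(Z < −1.645 − 0.72) ≈ 0.178 + 0.009 = 0.187.
- For 6/6.5/7 days: variance 4 + 1/6 = 4.17, SE 0.532, ratio 0.204/0.532 = 0.38, giving 0.104 + 0.021 = 0.125.

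**Simulation (4,000 trials per 5/6/7 scenario, gamma-distributed stay).** The equal-mix 5/6/7 case gives 17.5% (t-test) and 17.4% (Wilcoxon), close to the hand result.

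| Setting, SD 2 days, no POAF effect | Significant at 0.10 | Spurious gap |
|---|---|---|
| Equal stays in all operations (control) | 10.8% (t), 10.1% (Wilcoxon) | 0.01 day |
| 6/6.5/7 days, across mixes | about 10–14% | from about 0.14 day |
| 5/6/7 days, across mixes | about 13–22% | about 0.3–0.5 day |
| 5/6/7 days, linear model with operation and arm | 9.5–10.3% | – |
| 5/6/7 days, randomised arms, unadjusted | 9.3–10.5% | – |

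**Sensitivity to SD, 5/6/7 days.** At SD 3 the rate is 12–17%; at SD 1 it is 20–38%. The protocol gives no SD, so the size cannot be fixed more closely. Across all SDs the adjusted model stays at 9.2–10.8%.

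**Re-operation.** The protocol gives no re-operation rate, overall or by operation, so no comparable calculation is possible. What remains is order of events. Background lists surgical trauma and inflammation among the causes of POAF that have been examined, so a re-operation could come before POAF. The institution's practice is to anticoagulate persistent or recurrent POAF, so bleeding could also follow it. A two-group test does not distinguish the two.

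**The case against.** The strongest reply is that the plan asks only whether there is a difference. In the scenarios above the groups really do differ, because their operations differ, so a significant result answers the question as written. The trial's stated hypothesis concerns the maze and POAF incidence; no decision depends on this test, and nothing says it will support the economic argument. This largely stands. A reader might infer that the plan sets out to declare a causal effect of POAF; the text does not say so. What survives is narrower: the comparison has the same test and level as the randomised one, with no label or adjustment to separate them, in a document that already treats the link as causal.

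Three other stronger readings are tempting.

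- **That longer monitoring largely creates the association.** Telemetry runs to discharge, and a constant POAF hazard until then would give false-positive rates of roughly 19–73% for SDs of 1 to 3 days. But the protocol puts the peak of risk at 48 to 96 hours, inside the usual stay, and POAF follow-up continues after discharge. That calculation is an upper bound, and the real effect should be limited.
- **That re-operation is confounded by operation type just as stay is.** No re-operation rates are given, so this is not shown.
- **That the bias is large.** The highest rates need an SD of 1 day. A spurious gap of at most about 0.5 day is also well short of the two to four days that Background attributes to POAF.

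It is also fair to say that confounding by operation does not require dropping the p-value, since adjustment corrects it. Adjustment does not settle which event came first.

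**Conclusion.** The concern holds in a limited form. On the protocol's own statements operation type is related to both POAF and stay, so the unadjusted comparison of stay by POAF status is confounded and cannot show that POAF prolongs stay. With no POAF effect, SD 2 days and mean stays within 5 to 7 days, the test is significant in about 10–22% of trials against a nominal 10%, with a spurious gap of about 0.1–0.5 day. The direction follows from the documents if the operations with more POAF also have the longer stays; the size rests on the assumed SD, operation mix and stay by operation. For re-operation the weakness is the unknown order of events, and no size can be given. This is a minor, worthwhile correction to a secondary analysis in a feasibility study. The primary POAF test and the randomised comparisons are not affected.

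**What to change.** In Statistical Methods, separate the two comparisons.

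1. State that the comparison of randomised arms is the inferential test for the secondary outcomes.
2. For stay by POAF status, either report it descriptively by arm and operation type, or fit a model adjusted for operation type and arm. In either case label the result an exploratory association that does not estimate the effect of POAF.
3. For re-operation for bleeding by POAF status, report counts descriptively. Use the POAF date (Data management) and the adverse-event onset date (Adverse events) to separate re-operations before POAF from those after it.

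The cost is a few sentences of plan wording. Operation type, arm, length of stay and both dates are already to be recorded. The downside is one fewer secondary p-value, or a slightly less precise one if the model is used.
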